# 6.5. Subject Withdrawal

Withdrawal of consent: caregivers/subjects who request to discontinue study treatment will remain in the study and must continue to be followed for protocol specified follow-up procedures. The only exception to this is when the caregiver/subject specifically withdraws consent for any further contact with him or her or persons previously authorized by the subject to provide this information. Caregiver/subjects should notify the investigator in writing of the decision to withdraw consent from future follow-up, whenever possible. The withdrawal of consent should be explained in detail in the medical records by the investigator, as to whether the withdrawal is only from further receipt of study drug or also from study procedures and/or post treatment study follow-up, and entered on the appropriate

CRF page. In the event that vital status (whether the subject is alive or dead) is being measured, publicly available information should be used to determine vital status only as appropriately directed in accordance with local law.

Subjects may withdraw from the study at any time at their own request, or they may be withdrawn at any time at the discretion of the investigator or sponsor for safety or behavioral reasons, or the inability of the subject to comply with the protocol required schedule of study visits or procedures at a given study site.

If a subject does not return for a scheduled visit, every effort should be made to contact the subject. In any circumstance, every effort should be made to document subject outcome, if possible. The investigator should inquire about the reason for withdrawal, request that the subject return all unused study drug, request the subject to return for a final visit, if applicable, and follow-up with the subject regarding any unresolved AEs. The clinical staff will make every effort to contact subjects 28 days following their last dose to ascertain health status (ie, AE/suicidality).

Subjects who do not reach a stable dose by Visit 4 (Day 28) will be discontinued from the study. Subjects who have illicit substances at Screening on the UDT will be discontinued from the study, unless supported by prescription for medicinal use. Those subjects who discontinue the study early and do not complete 2 weeks of the Maintenance Phase should return to the study center as soon as possible for PK sampling and Early Termination procedures.

If the subject withdraws from the study, and also withdraws consent for disclosure of future information, no further evaluations should be performed, and no additional data should be collected. The sponsor may retain and continue to use any data collected before such withdrawal of consent.

In the event of clinically important treatment-emergent suicidal ideation or suicidal behavior, the subject will be withdrawn from the study and will receive the appropriate medical care, which may include medication. The investigator will follow up until the subject's condition has stabilized. Additionally, a risk assessment or evaluation of suicide risk will be completed by a child and adolescent mental health provider as part of the psychiatric evaluation and assessment of subject safety. Refer to Section 7, Assessments. Clinically important suicidality includes but is not limited to:

- 1. Suicidal behavior (with or without intent of suicide or serious self-harm).
- 2. Determination of 'yes' on question 4 (Active Suicidal Ideation with Some Intent or Act, Without Specific Plan) for the Suicidal Ideation section of the C-SSRS.
- 3. Determination of 'yes' on question 5 (Active Suicidal Ideation with Specific Plan and Intent) for the Suicidal Ideation section of the C-SSRS.

- 4. Determination of 'yes' on the question of Actual Attempt, Interrupted Attempt, Aborted Attempt, or Preparatory Acts or Behavior for Suicidal Behavior section of C-SSRS.
- 5. Acute suicidality to such a degree that precaution against suicide must be exercised.

### 6.6. Lost to Follow-Up (LTFU)

All reasonable efforts must be made to locate subjects to determine and report their ongoing status. This includes follow-up with persons authorized by the subject as noted above. Lost to follow-up is defined by the inability to reach the subject after a minimum of 2 documented phone calls, faxes, or e-mails as well as lack of response by the subject to 1 registered mail letter. All attempts should be documented in the subject's medical records. If it is determined that the subject has died, the site will use permissible local methods to obtain the date and cause of death. If the investigator's use of a third-party representative to assist in the follow-up portion of the study has been included in the subject's informed consent, then the investigator may use a sponsor-retained third-party representative to assist site staff with obtaining the subject's contact information or other public vital status data necessary to complete the follow-up portion of the study. The site staff and representative will consult publicly available sources, such as public health registries and databases, in order to obtain updated contact information. If, after all attempts, the subject remains lost to follow-up, then the last-known-alive date as determined by the investigator should be reported and documented in the subject's medical records.

A subject will be considered LTFU when one or more Treatment Period visits are missed AND attempts to contact the subject have been unsuccessful leading to an outcome of a missed Visit 6 visit. The following attempts must be made in the order listed below:

- 1. 3 documented\* attempts via telephone; then
- 2. 1 documented\* trip by study center personnel to a subject's last known address; then
- 3. 1 certified, receipted postal letter.

**Note:** A subject who does not return to study but does eventually respond to a site's attempts and is known to be in general good health will be considered as "no longer willing to participate in the study".

#### 6.7. Unscheduled Visits for Pain, Adverse Events

If at any time pain increases during the Treatment Period, rescue medication therapy is preferred, which includes IR morphine as necessary. For unscheduled visits due to an increase in pain where up-titration is necessary, record at a minimum, the Numeric Rating Scale (NRS) pain and COWS scores on the appropriate CRF in addition to any related CRF (eg, concomitant medications, dosing log). An unscheduled visit for any other reason (most typically an AE) will require the Visit 6/ET procedures to be performed (Schedule of

\* Receipts, dates and times must be documented in source documents.

Activities). An unscheduled visit due to a combination of an AE and an increase in pain requires the Visit 6 procedures.

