# **SCHEDULE OF ACTIVITIES**

The Schedule of Activities table provides an overview of the protocol visits and procedures. Refer to STUDY PROCEDURES and ASSESSMENTS sections of the protocol for detailed information on each procedure and assessment required for compliance with the protocol.

The investigator may schedule visits (unplanned visits) in addition to those listed on the schedule of activities, in order to titrate study drug or conduct evaluations/assessments required to protect the wellbeing of the subject.

Periods		Screening	eening Treatment								
		(2 Wks)	Conversion/Titration Phase (1 to 4 Wks)					Ma	Follow Up//EOS (Clinic) (1 Wk)		
its	Visit	1	2	3a 	3b 	3c 	$3d^2$	4	5	6/ET	7
Scheduled Visits	Day ±Allowable Window	-14 to -1	1	7±2	NR	NR	NR	21±2	35±2	49±2	56±2
Inled					14±2	NR	NR	28±2	42±2	56±2	63±2
ched						21±2	NR	35±2	49±2	63±2	70±2
Š							28±2	42±2	56±2	70±2	77±2
	Activities										
Informed Consent/Assent 		X									
Inclus	sion/Exclusion Criteria (Sections 4.1 and 4.2)	X									
Demo	ographics	X									
Medi	cal History	X									
Opioi	d Therapy Review	$x^4$	$X^{5}$								
	Physical Examination (Section 7.2.6)	X								X	
	Clinical Laboratory Tests (Section 7.2.3)	X								X	
8.	Pregnancy Test (Section 7.3)	$X^{6}$	<				X 		>	$X^{6}$	
Safety	Urine Drug Test (Section 7.2.7)	X									
N	Single, 12–lead ECG  (Section 7.2.4)	X									
	Vital Signs (Section 7.2.2)	X	X	X	X	X	X	X	X	X	
	Suicide Ideation and Behavior (SIB)	X	X	X	X	X	X	X	X	X	X

Periods		Screening Treatment									Post-Treatment
		(2 Wks)	Conversion/Titration Phase (1 to 4 Wks)					Ma	Follow Up//EOS (Clinic) (1 Wk)		
its	Visit	1	2	3a 	3b 	3c 	3d 	4	5	6/ET	7
Scheduled Visits	Day ±Allowable Window	-14 to -1	1	7±2	NR	NR	NR	21±2	35±2	49±2	56±2
nled					14±2	NR	NR	28±2	42±2	56±2	63±2
pəq						21±2	NR	35±2	49±2	63±2	70±2
S							28±2	42±2	56±2	70±2	77±2
	Activities										
	Assessment (Section 7.4.1)										
	COWS (Section 7.2.5)	X	X	X	X	X	X	X	X	X	
	Concomitant Medication (Section 5.7)	X	X	X	X	X	X	X	X	X	
	Adverse Events  (Section 7.2.1)	X	X	X	X	X	X	X	X	X	X
	Pain Intensity (In-Clinic) (Section 7.1.1)		X	X	X	X	X	X	X	X	
Treatment Response	Review Diary Information 11			X	X	X	X	X	X	X	
odsa	Pain Intensity (Diary Review)			X	X	X	X	X	X	X	
t Re	Rescue Medication (Diary Review)			X	X	X	X	X	X	X	

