nen	Concomitant Medication (Diary Review)			X	X	X	X	X	X	X	
eatı	Study Drug Use (Diary Review)			X	X	X	X	X	X	X	
Ţ	Adverse Events (Diary review)			X	X	X	X	X	X	X	
	Plasma Sample (Section 7.5.2) 							X		X 	
Careg	iver Training and Subject Instruction		X								
Dose	Conversion Calculation 		X								
Dispe	nse Study Drug		X	X	X	X	X	X	X		
Prescribe Rescue Medication (as necessary)			X	X	X	X	X	X	X	X	
Dose Titration (as needed)				X	X	X	X				
Drug Accountability				X	X	X	X	X	X		
Early Withdrawal Subjects 										X	
Weekly Telephone call 			<						· 		>

Min = Minimum; Max = Maximum; NR = Not Required; EOS = End of Study; ECG = Electrocardiogram; ET = Early Termination; COWS = Clinical Opiate Withdrawal Scale; PK = Pharmacokinetics, Wks= Weeks

- 1. Visit 3a is a mandatory visit.
- 2. Visits 3b, 3c, and 3d are required only if further dose titrations are required to reach a stable dose. Subjects must reach a stable dose of PF-06412528 on or before Visit 3d to be eligible to start the 6-week Maintenance Phase. Unscheduled visits during the Treatment Period for purposes of dose adjustment will, at a minimum, require a NRS pain scale and a COWS score on subjects. An unscheduled visit for an AE will require performing the Visit 6 procedures.
- 3. Informed consent must be provided by the subject's caregiver (parent or legal guardian). Subjects are required to provide their assent.
- 4. Review the subject's pre-study standard of care (SOC) therapy and record on the appropriate case reporting form.
- 5. SOC therapy is required to stop on this visit. Record these changes on the appropriate case reporting form.
- 6. Serum pregnancy test for a qualified female of childbearing potential (Section 7.3).
- 7. Urine pregnancy test for a qualified female of childbearing potential (Section 7.3).
- 8. ECGs performed post-baseline are acceptable when performed "for-cause".
- 9. Refer to Section 7.4.1 for the correct Columbia-Suicide Severity Rating Scale to apply for a given age group.
- 10. Record serious adverse events from the signing of the informed consent. Non-serious AEs are recorded from first dose of study drug. Review and transcribe Caregiver adverse findings from the Daily Diary to the appropriate case reporting form. Follow up on all SAEs through and including 28 calendar days post the last dose of study drug (Section 8.2). Follow up requirements for non-serious AEs (Section 8.1).

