# 3.2.1. Conversion/Titration Phase (Visits 2-3d)

Subjects and their caregiver(s) will report for weekly visits during this 1-4 week period to convert their current standard of care opioid therapy for pain management to PF-06412528. The goals of the Conversion/Titration Phase are to convert subjects from their pre-study standard of care opioid analgesic to PF-06412528 and to individualize pain management by titrating PF-06412528 (Visits 2-3d; see Schedule of Activities) to achieve a stable dose. A stable dose is characterized as a dose that provides adequate analgesia and minimizes adverse reactions for 5 to 7 days. During Visit 2 the subject's study eligibility will be verified, the subject's current standard of care opioid therapy will be discontinued and PF-06412528 will be initiated at a dose determined using the PF-06412528 Conversion Guide (Appendix 2).

Four weekly scheduled study visits (Visits 3a-3d) are planned to provide enough time to individualize pain management with PF-06412528. Visit 3a is mandatory for all subjects and Visits 3b, 3c, and 3d are optional, if additional dose titration is needed. Visits 3b or 3c or 3d can be skipped if a subject reaches a stable dose at a prior visit. When a stable dose is achieved, the subject advances to the Maintenance Phase at the next visit (Visit 4). More frequent consultation with the investigator as well as additional unscheduled clinic visits are permitted, as needed (eg, to titrate study drug). All information about the dosing of PF-06412528 (ie, dosage strength, frequency of dosing, and daily schedule) will be obtained and recorded at each scheduled/unscheduled visit.

The Conversion/Titration Phase will end once a PF-06412528 dose that provides adequate analgesia and minimizes adverse reactions is achieved (ie, stable dose) with infrequent need for IR morphine as rescue as determined by the investigator. Subjects who do not reach a stable dose without the need for IR morphine as rescue by Visit 3d, will be removed from treatment and converted back to their previous opioid therapy or another therapy at the discretion of the investigator.

The start of the Maintenance Phase will begin once a subject has achieved a stable dose of PF-06412528 and the next study visit (Visit 4) will be scheduled in two weeks' time.

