# 3.2.2. Maintenance Phase (Visit 4-6)

The goal of the Maintenance Phase is to characterize the PK under steady-state study conditions as well as demonstrate the safety of PF-06412528 over a 2-6 week period. If at Visit 4 subjects require additional pain relief in the opinion of the investigator, they will continue in the study for an additional 2-4 weeks (Visit 5 and/or Visit 6) up to 6 weeks total.

Daily Diary and in-clinic pain intensity and safety will be assessed at each visit to determine if any dose adjustments are required. Rescue medication (acetaminophen and/or NSAID's) is permitted during this phase. IR morphine for rescue is discouraged during the Maintenance Phase.

Blood samples will be collected for PK analysis at Visit 4 for those subjects that achieve a stable dose between Visits 3a-d. Two blood samples will be taken at least two-hours apart at Visit 4. If for any reason PK samples are not obtained at Visit 4, the subject should return to enable them to be obtained at an unscheduled visit.

At the final Maintenance Phase visit (Visit 4 or 5 or 6), the investigator will discontinue the subject's PF-06412528 therapy and convert the subject back to their standard of care of opioid therapy. Blood samples will be collected for PK analysis if not already obtained. A Post-Treatment/End of Study visit will be scheduled in 7 ±2 days (Visit 7).

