# • Assess Treatment Response:

- Pain intensity (Diary Review and in-clinic assessment);
- Rescue Medication (Diary Review);
- Concomitant Medication (Diary Review);
- Study Drug Use (Diary Review);
- Adverse Events (Diary Review).
- COWS Assessment.
- Concomitant Medication Assessment.
- Adverse Event Assessment.
- **Pregnancy Test:** Take a urine sample from all females of childbearing potential.
- **Vital Signs:** Record blood pressure, pulse rate, and respiration.
- SIB Assessment: C-SSRS (Section 7.4.1):
  - Children's Since Last Visit (Ages 7-11) (Version 6/23/10)-(Appendix 5).
  - Since Last Visit (Ages 12-17) (Version 1/14/09)-(Appendix 6).
- Drug Accountability: See Section 5.6.
- **Dose Titration:** Adjust PF-06412528 dosage as needed to optimize pain therapy.
- **Prescribe Rescue Medication (if needed):** Prescribe rescue medication (acetaminophen and/or NSAID's) to be used during conversion and titration.
- **Dispense Study Drug** (PF-06412528) to caregiver.

**For Converted Subjects:** If, at this visit, the subject has been fully discontinued from the standard of care opiate therapy and successfully titrated to a stable dose of PF-06412528 and with infrequent use of IR morphine for rescue the subject may be scheduled for the next visit, which will be Visit 4 (Schedule of Activities). It is at this visit (Visit 3a) the subject enters the Maintenance Phase of the Treatment Period.

**For Non-Converted Subjects:** If, at this visit, the subject **has not** achieved a stable dose of PF-06412528, this subject will remain in the Conversion/Titration Phase, therefore:

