### Visit 3b (Day $14 \pm 2$ days)

• Follow the same procedures and assessments as described at Visit 3a.

**For Converted Subjects:** If, at this visit, the subject has been fully discontinued from the standard of care opiate therapy and successfully titrated to a stable dose of PF-06412528 and with infrequent use of IR morphine for rescue the subject may be scheduled for the next visit, which will be Visit 4 (Schedule of Activities). It is at this visit (Visit 3b) the subject enters the Maintenance Phase of the Treatment Period.

**For Non-Converted Subjects:** If, at this visit, the subject **has not** achieved a stable dose of PF-06412528, this subject will remain in the Conversion/Titration Phase, therefore:

• Schedule the Visit 3c (Day 21 ±2) visit.

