### 7.2.2. Vital Signs

Vital signs, including resting systolic and diastolic blood pressure, pulse, and respiratory rate, are performed at designated study visits as outlined in the Schedule of Activities.

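### An unscheduled clinic visit to raise the dose for pain requires only a pain score and COWS, not the respiratory rate and blood pressure required at Visits 3a-3d

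*Protocol*

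**What the plan says.** Unscheduled titration visits are foreseen. Protocol Section 3.2.1 states: "More frequent consultation with the investigator as well as additional unscheduled clinic visits are permitted, as needed (eg, to titrate study drug". The introduction to the Schedule of Activities states: "The investigator may schedule visits (unplanned visits) in addition to those listed on the schedule of activities, in order to titrate study drug". The same sentence goes on to allow such visits for evaluations needed to protect the child.

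The minimum content of a dose-adjustment visit is given twice. Section 6.7, on visits for increased pain, reads "where up-titration is necessary, record at a minimum, the Numeric Rating Scale (NRS) pain and COWS scores on the appropriate CRF", together with related CRFs such as the dosing log. Schedule footnote 2 reads "Unscheduled visits during the Treatment Period for purposes of dose adjustment will, at a minimum, require a NRS pain scale and a COWS score". Section 7.3 adds a urine pregnancy test at unscheduled visits for females of childbearing potential.

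On vital signs, Section 7.2.2 reads "Vital signs, including resting systolic and diastolic blood pressure, pulse, and respiratory rate, are performed at designated study visits", with the Schedule as the reference for which visits those are. The Visit 3a procedures in Section 6.2.1 say "Record blood pressure, pulse rate, and respiration", and Visits 3b, 3c and 3d each say "Follow the same procedures and assessments as described at Visit 3a". Under Section 6.7, an unscheduled visit for any other reason, or for pain combined with an adverse event, requires the Visit 6 procedures, which include vital signs.

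For Maintenance, Section 3.2.2 says: "Daily Diary and in-clinic pain intensity and safety will be assessed at each visit to determine if any dose adjustments are required". It does not name the readings that make up the safety assessment.

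**The concern.** The visit at which opioid exposure is deliberately increased carries the lightest stated requirement. A scheduled titration visit needs blood pressure, pulse and respiration. An unscheduled visit for a reason other than pain needs the full Visit 6 set. An unscheduled visit for pain with up-titration needs a pain score and a withdrawal score.

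Section 5.1.2 lists reduced respiratory rate and hypotension among the signs of morphine overdose. COWS is built to detect the opposite state and does not measure either. Its pupil item gives the same score of 0 to a pinned pupil and a normal one, so a classic sign of opioid excess leaves the total unchanged.

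What is at stake is early toxicity, not yet recognised as an adverse event, in a child who presents with more pain. Section 6.7 prefers rescue medication first, and that may include IR morphine, so such a child may already have taken extra opioid. Section 5.4 allows dose changes every 1 to 2 days, so more than one increase could fall between scheduled readings.

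**Working it through.** The plan gives no figure to reproduce. The check compares requirements, followed by simple counts and date arithmetic.

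**1. Required assessments by type of visit**

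| Visit | Required on this point | Respiratory rate and BP required? |
|---|---|---|
| Scheduled titration, Visits 3a-3d (Section 6.2.1, Schedule) | Pain, COWS, AE assessment, BP, pulse, respiration | Yes |
| Unscheduled, AE or AE plus pain (Section 6.7) | Visit 6 procedures | Yes |
| Unscheduled, pain with up-titration, no AE identified (Section 6.7, footnote 2) | Pain score, COWS, related CRFs; pregnancy test where applicable | No |

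**2. Could another section supply the readings?** Section 7.2.2 defers to the Schedule, which has no column for unplanned visits. Section 7.3 expressly extends pregnancy testing to unscheduled visits; Section 7.2.2 has no matching extension. Section 3.2.2 covers Maintenance only and names no reading. SAP Section 8.1.7 summarises vital signs by visit and adds no collection. No other source was found.

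**3. What COWS contributes.** Section 7.2.2 names systolic BP, diastolic BP, pulse and respiratory rate: 4 readings. The 11 COWS items (Appendix 8) include resting pulse and none of the others: 1 captured.

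- Not required: 4 − 1 = 3 of 4.
- Counting blood pressure once, as Visit 3a does: 3 − 1 = 2 of 3.

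**4. Spacing of scheduled vital signs around such a visit.** Nominal gap = later day − earlier day. Maximum gap = (later day + 2) − (earlier day − 2), except that Day 1 has no window.

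| Interval | Nominal (days) | Maximum (days) |
|---|---|---|
| Day 1 to Visit 3a | 7 − 1 = 6 | 9 − 1 = 8 |
| Visit 3a to 3b | 14 − 7 = 7 | 16 − 5 = 11 |
| Visit 3b to 3c | 21 − 14 = 7 | 23 − 12 = 11 |
| Visit 3c to 3d | 28 − 21 = 7 | 30 − 19 = 11 |
| Visit 3a to 4 (Maintenance) | 21 − 7 = 14 | 23 − 5 = 18 |
| Visit 4 to 5 | 35 − 21 = 14 | 37 − 19 = 18 |
| Visit 5 to 6 | 49 − 35 = 14 | 51 − 33 = 18 |

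The Maintenance rows use the Visit 3a entry route. The later routes shift every day by the same amount and give the same gaps. These gaps describe the spacing of measured vital signs, not time without any safety contact.

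**The case against.** The strongest reply is that the list is only a floor and other safeguards surround it. The Schedule introduction lets the investigator add any assessment needed to protect the child. COWS is administered by a clinician, who will see somnolence, cyanosis or constricted pupils whatever they score. Section 8.13 requires questioning about adverse events, and a recognised event brings in the Visit 6 procedures. Caregivers are trained to recognise toxicity and to seek help at once, and sites telephone weekly. Subjects are opioid-experienced, the starting dose is generally halved, and rescue is preferred to up-titration. Further, no rule at Visits 3a-3d makes a dose increase depend on a vital-sign threshold, so those readings could be seen as data collection rather than a dosing safeguard. The proposed fix also leaves increases made without a clinic visit untouched.

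Much of this stands, and it is why the gap is narrow. It does not close the gap. Permission to measure is not a requirement, and a protocol minimum is what every site must do. The adverse-event route works only once toxicity is recognised, and a reduced respiratory rate can be missed unless it is counted. It is true that no threshold is attached at Visits 3a-3d, but dose titration and vital signs are listed in the same set of procedures there, so the investigator has the readings when deciding. The limit on increases made away from clinic is accepted: the fix covers the visit where the omission is easily corrected.

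**Conclusion.** The concern holds. At an unscheduled in-clinic visit for pain with up-titration and no identified adverse event, respiratory rate and blood pressure are not required, although scheduled visits for the same decision require both. Three of the four Section 7.2.2 readings are missing from the minimum, or two of three if blood pressure is counted once.

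This rests on reading the minimum as written; sites may do more. The documents do not say how often such visits are expected, so the number of children affected cannot be estimated, and no probability of missed toxicity is claimed. Scheduled vital-sign data and their by-visit summaries are unaffected, and no trial estimate changes. It is a patient-safety improvement worth making because it is so cheap, not a threat to the study's conclusions.

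**What to change.** In Section 6.7 and in Schedule footnote 2, extend the minimum for an unscheduled in-clinic up-titration visit to pain score, COWS and the vital signs defined in Section 7.2.2 (blood pressure, pulse and respiratory rate), recorded before the dose is raised. This brings the visit into line with Visits 3a-3d on vital signs. It adds no sedation scale, changes no adverse-event or dosing rule, and places no requirement on increases made without a clinic visit.

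The cost is a few minutes per visit and minor protocol and CRF wording. Pulse is already taken for COWS, so only respiratory rate and blood pressure are new. No extra visit, staff or equipment is needed.
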